## **9.8 Criteria for Early Termination of Study Participation other than HIV-1/2 Infection and Pregnancy**

Participants may voluntarily withdraw from the study for any reason at any time. The IoR/designee also may withdraw participants from the study to protect their safety and/or if they are unwilling or unable to comply with required study procedures, after consultation with the PSRT. Participants also may be withdrawn if NIAID, MTN, government or regulatory authorities including the Office for Human Research Protections (OHRP), or site IRBs/IECs terminate the study prior to its planned end date. Every reasonable effort is made to complete a final evaluation of participants who withdraw or are withdrawn from the study prior to completing follow-up (see details regarding the Early Termination Visit in [Section 7.4.3](#)). Study staff members will record the reason(s) for all withdrawals in participants' study records.

# **10 STATISTICAL CONSIDERATIONS**

## **10.1 Overview and General Design**

This is a multi-site, randomized-sequence, three-period, open label crossover study designed to compare acceptability, tolerability, safety, and adherence data within individuals who have been exposed to an insert, a douche and a suppository applied rectally and used prior to RAI. Approximately 210 HIV-uninfected participants will be randomized to receive one of six study product application sequences. In the first product use period, participants will use either the rectal insert, the rectal douche, or the rectal suppository prior to RAI during a 4-week-long period. After a 1-week washout period, they will use one of the other two study products prior to RAI during the second 4-week-long study product use period. After another 1-week washout period, they will use the remaining study product prior to RAI during the third 4-week-long study product use period.

## **10.2 Study Endpoints**

Consistent with the primary study objective to evaluate the acceptability and tolerability of a placebo insert, a placebo douche, and a placebo suppository when applied rectally and used prior to RAI, the following endpoints will be assessed on a scale of 1 to 10 for each study product:

- Participant self-report of likelihood of product use if shown to be effective

Consistent with the primary study objective to evaluate adherence to a placebo insert, a placebo douche, and a placebo suppository when applied rectally and used prior to RAI over a 4-week-long period, the following endpoints will be assessed for each study product:

- Per participant report, percentage of occasions when study product was used as instructed (per protocol)

Consistent with the primary study objective to evaluate the safety of a placebo insert, a placebo douche, and a placebo suppository when applied rectally and used prior to RAI, the following endpoints will be assessed for each study product:

- Grade 2 or higher related AEs as defined by the Division of AIDS Table for Grading the Severity of Adult and Pediatric Adverse Events, Corrected Version 2.1, July 2017, and/or Addenda 1, 2 and 3 (Female Genital [Dated November 2007], Male Genital [Dated November 2007] and Rectal [Clarification Dated May 2012] Grading Tables for Use in Microbicide Studies)

### **10.3 Sample Size and Power**

There is no control group for comparison in this study. The goal is not to compare each product to some standard but instead to estimate overall rates of acceptability, adherence and safety.

#### **10.3.1 Primary Endpoints – Acceptability/Tolerability and Adherence**

Based on previous studies we expect to observe a high rate of acceptability (>80%) which equates to  $\leq 20\%$  of participants reporting a low likelihood of using the product in the future ( $\leq 3$  on the rating scale). Likewise, we expect to observe a high rate of participants reporting taking at least 90% of expected doses.

The table below shows the exact confidence intervals for acceptability and adherence, assuming  $\alpha=0.05$  based on the Binomial distribution and varying rates of acceptability and adherence. The power to rule out  $<50\%$  and  $<70\%$  acceptability or adherence given the rates is also shown. Calculations assume the outcomes are observed in 200 of the participants (5% loss to follow-up). For example, if the true acceptability or adherence rate is 90%, we have 100% power to rule out a true acceptability or adherence rate of 75% or lower. If we observe an 80% acceptability or adherence rate, the corresponding 95% confidence interval (CI) will be (74%, 85%).

**Table 9: Exact 2-sided 95% Confidence Intervals Based on Various Rates of Acceptability or Adherence Endpoints**

Acceptability rate / adherence rate	95% CI if rate is observed	Power to rule out 50% if rate is true	Power to rule out 70% if rate is true	Power to rule out 75% if rate is true
95%	(91, 98)	100%	100%	100%
90%	(85, 94)	100%	100%	100%
85%	(79, 90)	100%	100%	93%
80%	(74, 85)	100%	90%	35%

### 10.3.2 Primary Endpoint – Safety

To characterize the statistical properties of the safety endpoint, the table below presents the probability of observing zero, at least one, and two or more safety endpoints among 200 participants (allowing for the possibility of 5% dropout) assuming various “true” event rates. By assuming that we may only have safety evaluations on 200 participants, these calculations are conservative. However, safety analyses will include all enrolled participants.

**Table 10: Analysis of Safety Event Frequency**

Event Rate	P(0 events   n=200)	P( $\geq 1$ event   n=200)	P( $\geq 5$ events   n=200)	P( $\geq 10$ events   n=200)
0.1%	82%	18%	0%	0%
0.5%	37%	63%	0%	0%
1%	13%	87%	5%	0%
2%	2%	98%	37%	1%
5%	0%	100%	97%	55%

### 10.4 Randomization Procedures

Participants will be randomly assigned with the ratio 1:1:1:1:1:1 to one of six study product application sequences. The randomized assignments will be in blocks to keep the balance of equal allocation. The randomization scheme, including enrollment of replacement participants, will be generated and maintained by the MTN SDMC.

### 10.5 Participant Accrual and Retention

The accrual period is expected to require approximately 9-12 months. The study will enroll approximately 210 participants.

The target retention rate for each study visit is 95%. Therefore, once a participant is enrolled in the study, the study site will make every reasonable effort to retain the participant for the entire study duration so that the participant is evaluable.

### 10.6 Data and Safety Monitoring Procedures

No Data and Safety Monitoring Board oversight is planned for this study. The MTN Study Monitoring Committee (SMC) will conduct interim reviews of study progress, including

rates of participant accrual, retention, completion of primary endpoint assessments, and study or lab issues by arm of the study. These reviews will take place approximately every 4-6 months, or as needed. Reviews may also be conducted on an as needed basis. At the time of this review, or at any other time, the SMC may recommend that the study proceed as designed, proceed with design modifications, or be discontinued.

## **10.7 Data Analyses**

### **10.7.1 Primary Analyses on Acceptability/Tolerability and Adherence Measures**

All primary analyses will be based on data from the participants with data in all three periods of study (participants who complete each period of the study). Baseline values between these participants and those participants lost to follow-up will be described and used to interpret the generalizability of the results. Additionally, secondary analyses will analyze endpoints among all participants. The adherence and acceptability/tolerability endpoints (defined in Section 10.3.1) will be reported with 95% CI. The purpose of this protocol is not to compare the placebo products; therefore, we do not plan on doing comparisons between products in the primary analysis. Logistic regression models will be used to assess the order of product use (period effect) on acceptability/tolerance and adherence.

### **10.7.2 Primary Analysis on Safety Measures**

All visits in which a participant has been exposed to the study product will be included in the primary analyses of safety. Secondary analyses including the washout period may also be performed. The number and the percentages of participants experiencing each safety endpoint (see Section 10.2) will be tabulated by study arm. Each participant will contribute once in each category (i.e., only for highest severity AE for each participant) for the calculation of event rates. Exact binomial confidence intervals will be calculated for each safety endpoint for each arm and Fisher's Exact test will be used to test for differences in event rates between the arms. Logistic and Poisson regression models will be used to assess the order of product use (period effect) on safety endpoints.

## **10.8 Missing Data**

A retention rate of 95% is targeted. Based on previous MTN trials, minimal missing data is expected. If missing data rates are higher than anticipated (over 10%), sensitivity analyses will be conducted to assess the impact of missing data on trial inference. Assuming missing data are ignorable, we will use multiple imputation based on all available baseline predictors and available trial outcomes.

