3. GENERAL DATA ANALYSIS CONSIDERATIONS

3.1 Analysis Set(s)

Safety endpoints will be assessed on a modified intent-to-treat analysis set, which will include all participants enrolled in the study who received at least one of the study products during the study. Primary acceptability, tolerability and adherence endpoints will be assessed on a per-protocol (PP) analysis subset, which will consist of participants who received all three study products and completed the corresponding product use end visits (PUEVs).

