3.2 Statistical Analysis Issues

A retention rate of 95% is targeted. Based on previous MTN trials, minimal missing data is expected. If missing data rates are higher than anticipated (over 10%), sensitivity analyses will be conducted to assess the impact of missing data on trial inference. If missing data rates are over 10 and assuming missing data are ignorable, we will use multiple imputation based on all available baseline predictors and available trial outcomes. Otherwise, we will complete analyses using available data.

For primary safety analysis, safety endpoints will be classified by the product used at that particular period, starting from date of enrollment or most recent product switch visit. If a participant did not receive a particular product then that participant-period will be excluded from the analysis. Due to COVID-19, some participants have received multiple products in advance or have received product through mail. The actual product switch visit date for the corresponding product will be used as the start of the product use period instead of the date participants received the product. A safety endpoint will be considered to have occurred during a specific product use period if the onset date of the AE is on or after start of the product use period (enrollment or switch visit date) and before the start of the next product use period (switch visit date or end of study).

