8. PRIMARY ENDPOINTS

The acceptability, tolerability and adherence primary endpoints will be evaluated on the per-protocol subset of participants, i.e. participants who received all three study products and completed the corresponding PUEV, and thus provide relevant data from all three periods of study. Assessment of these endpoints will be based on responses from the participants to the computer assisted self-interviews (CASI) at the three PUEVs (Visits 3, 5 and 7). To aid in the interpretation of the resulting analyses, baseline characteristics of the per-protocol subset of participants including, but not limited to, study site, sequence, sex/gender, and age will be described and compared to those of participants who were lost to follow-up.

Acceptability and Tolerability

The acceptability and tolerability endpoint will be based on question H1 of the CASI:

“Think about the positive and negative experiences you have had using the rectal Insert during the past 4 week period. If this rectal insert was available and it provided some protection against HIV, how likely would you be to use it before receptive anal sex?”.

Responses to this question for each product were captured from visual Likert scale from 1 (very unlikely) to 10 (very likely). Participants’ responses corresponding to the three product use periods will be displayed in tables by study product, by study product and site and by study product and randomization sequence.

To compare acceptability and tolerability between study products, the endpoint will be operationalized as binary, with scores 1 to 6 grouped as “low acceptability” and scores 7 – 10 as “high acceptability”. Number and percentage of participants giving a “high acceptability” score will be display in tables by study product, with exact binomial 95% confidence intervals (Clopper-Pearson method).

Adherence

Two endpoints related to adherence will be assessed: adherence to use per-protocol and adherence to use per-anal-sex-act. These are defined as follows:

1. **Adherence to use per-protocol:** Number and proportion of participants who reported not having missed a rectal [enema/douche, insert or suppository] application in the previous 4 weeks, according to the participants’ response to question B0 of the CASI:

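### The primary acceptability and adherence rates rest on completers, and no planned analysis allows for dropout linked to a dislike of the product that was never recorded

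*Protocol*

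**What the plan says.** **Analysis set.** Protocol 10.7.1 bases the primary acceptability and adherence analyses on participants with data in all three periods. SAP 3.1 defines the per-protocol set as "participants who received all three study products and completed the corresponding product use end visits (PUEVs"), and SAP 8 uses that set. Both endpoints come from the computer-assisted interview (CASI) at Visits 3, 5 and 7: item H1 for acceptability, and item B0 for adherence per protocol.

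**Missing data.** Protocol 10.8 promises sensitivity analyses if more than 10% of data are missing, and names one method: "Assuming missing data are ignorable, we will use multiple imputation based on all available baseline predictors and available trial outcomes". SAP 3.2 has the same rule: "If missing data rates are over 10 and assuming missing data are ignorable, we will use multiple imputation". At or below the trigger, the SAP falls back on available data. Neither document names a worst-case, delta-adjusted or tipping-point analysis.

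**Supporting analyses.** Protocol 10.7.1 adds a secondary analysis among all participants, with no trigger. The SAP does not specify it for acceptability or adherence. SAP 8 says that baseline characteristics of the per-protocol set "will be described and compared to those of participants who were lost to follow-up".

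**Stopping a product.** Under Protocol 7.5.3, a participant who stops by choice in period 1 or 2 may go on to the next product. One who stops by choice in period 3 is terminated from the study and offered an Early Termination Visit.

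**The concern.** Multiple imputation under ignorability allows for missingness that observed data can explain. It cannot show what happens when the missing answer itself is the reason for the absence. That is plausible here. A participant who rejects the third product and stops leaves the study, and may never answer H1 for that product. Protocol 7.8 assigns the CASI to the PUEVs and the conjoint assessment to the Final Visit. Without the third PUEV, that participant's valid ratings of the first two products also leave the primary set.

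The headline rates could therefore be too favourable, and no planned result would show by how much. The baseline comparison helps little. It covers those lost to follow-up, whereas the SAP 6.1.2 retention table counts missing visits separately from loss or termination. Someone excluded for one missed PUEV is not clearly included in the comparison.

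**Working it through.** **Inputs.**
- Enrolment: "The study will enroll approximately 210 participants" (Protocol 10.5).
- Evaluable number: "Calculations assume the outcomes are observed in 200 of the participants (5% loss to follow-up") (Protocol 10.3.1).
- Interval method: "Exact 2-sided 95% Confidence Intervals Based on Various Rates of Acceptability or Adherence Endpoints" (Protocol Table 9).
- Completer rate: 80%, an assumption taken from the planning statement "Based on previous studies we expect to observe a high rate of acceptability (>80"%). The Protocol's rate counts ratings above 3 and the SAP's counts 7 to 10, so 80% is illustrative only.

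**Step 1: reproduce the plan.** The Clopper-Pearson limits for x of n are the 2.5% quantile of Beta(x, n−x+1) and the 97.5% quantile of Beta(x+1, n−x). For 160/200 they are 73.8% and 85.3%; Table 9 prints (74, 85). Power is P(X ≥ r), where r is the smallest count whose lower limit exceeds the rate to be ruled out: r = 153 for 70% and r = 163 for 75%.
- True rate 80%, rule out 70%: 90.6% (Table 9: 90%).
- True rate 80%, rule out 75%: 33.5% (Table 9: 35%).
- True rate 85%, rule out 75%: 92.8% (Table 9: 93%).

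The method matches the plan's closely enough to use below.

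**Step 2: bounds.** Let m of 210 be missing, x be the completers rating high, and q the share of the missing who would have rated high. The rate over all 210 is (x + q·m)/210.

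| Missing | Completers | All missing counted low (q = 0) | All counted high (q = 1) |
|---|---|---|---|
| 10 (4.8%) | 160/200 = 80.0% (73.8 to 85.3) | 160/210 = 76.2% (69.8 to 81.8) | 170/210 = 81.0% |
| 21 (10.0%) | 151/189 = 79.9% (73.5 to 85.4) | 151/210 = 71.9% (65.3 to 77.9) | 172/210 = 81.9% |

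If the 10% is counted over participants, 21 of 210 is not over it and the trigger is not met. Between the extremes for those 21:
- q = 0.2: (151 + 4.2)/210 = 73.9%
- q = 0.4: (151 + 8.4)/210 = 75.9%
- q = 0.6: (151 + 12.6)/210 = 77.9%

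**Step 3: where the 70% benchmark tips.** With n = 210, a count of 160 has lower limit 69.8% and 161 has 70.4%. So 161 high ratings are needed to exclude 70%.
- 10 missing: 161 − 160 = 1. The conclusion tips only if none of the ten would have rated high.
- 21 missing: 161 − 151 = 10. It tips if fewer than 10 of the 21 (48%) would have rated high.

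**Step 4: a higher completer rate.** With 161/189 = 85.2% (79.3 to 89.9) and 21 missing, the worst case is 161/210 = 76.7% (70.4 to 82.2). The interval still excludes 70% but no longer excludes 75%.

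**Step 5: the trigger.** Neither document says whether the 10% is counted over participants, visits or items. Protocol 10.5 sets its 95% retention target per visit. If losses at the three PUEVs were independent (an assumption), 0.95³ = 85.7%, or about 180 of 210, would be complete. The trigger would then be met if counted over completers, although each visit met its target.

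**The case against.** The strongest reply is that the Protocol already looks beyond completers. The secondary analysis in 10.7.1 has no trigger and brings back low ratings given at an earlier PUEV by people who later left. Above the trigger, the imputation uses available trial outcomes, so recorded dislike can enter it. SAP 6.1.3, 6.1.4 and 6.2 tabulate reasons for stopping, reasons for non-completion, and PUEV completion by product. Other causes of loss are documented too: HIV infection, pregnancy, withdrawal for any reason, and COVID-19 disruption to product supply. The study also aims to estimate rates, not to test a product against a standard.

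Much of this stands, and it rules out several stronger readings that a reader might infer:
- *Dislike is never examined, or imputation is the only check.* Not so. Recorded dislike enters the all-participant analysis.
- *Anyone who stops a product is excluded.* Not so. The set depends on receipt and PUEV completion, so a participant who stops in period 1 or 2 and attends all three PUEVs stays in.
- *Imputation has nothing to act on in a completer set.* Neither document confines it to that set.
- *It is a fault that the sensitivity analysis cannot alter the primary estimate.* No sensitivity analysis does. The issue is the choice of completers.

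What the reply does not reach is dislike that was never recorded. Observed-answer analyses and imputation under ignorability both pass over it, and tables of reasons describe loss without showing its effect on the rate. The SAP, which sets out to describe the final primary and secondary analyses, leaves the all-participant analysis out for these endpoints.

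**Conclusion.** The point holds in this form: no planned analysis addresses non-ignorable dropout, and the Protocol's all-participant secondary analysis is not carried into the SAP for acceptability and adherence.

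As an extreme bound, the shift is 3.8 points at the planned 5% loss (80.0% to 76.2%) and 8.0 points at 10% loss (79.9% to 71.9%). In both cases a completer interval that excludes 70% no longer does. At 5% loss this requires every missing participant to be low; at 10% it requires fewer than 10 of 21 to be high.

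The figures rest on a completer rate near 80%. At about 85%, even the worst case at 10% loss still excludes 70%. A reader might take 72% as a likely result, but it is not. It scores all 21 excluded people low, although some would have an observed H1 answer for the product in question, and it uses 210 as denominator whether or not each person received that product. The documents do not show how much loss is product-driven, only that the design allows it. This is worth correcting, but it does not undermine the trial.

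**What to change.** In SAP 3.2 and SAP 8:

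1. Specify the all-participant secondary analysis by product, using every observed H1 and B0 answer.
2. With no 10% trigger, and among participants who received that product, report (i) missing H1 counted as low acceptability and missing B0 as not fully adherent, and (ii) a tipping-point table over the assumed success rate among the missing.
3. Keep multiple imputation as the ignorable-missingness version, on all randomised participants.
4. Compare baseline characteristics of the per-protocol set with all randomised participants outside it, not only those lost to follow-up.

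This is a cheap improvement. It needs no new data and adds about one table per endpoint. The downside is a pessimistic bound printed beside the headline rate, which should be labelled as a bound.

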# 11 DATA HANDLING AND RECORDKEEPING

## 11.1 Data Management Responsibilities

Data collection tools will be developed by the MTN SDMC in conjunction with the protocol team. Quality control queries will be routinely generated for study site verification and resolution. As part of the study activation process, the study site must identify all CRFs to be used as source documents. Study CRF data will be entered and cleaned using the Medidata Rave EDC tool, a data management system compliant with the International Council on Harmonization (ICH) Good Clinical Practices (GCP) and US CFR guidelines for electronic data capture.

Audio files generated by the in-depth interviews will be transcribed and translated into English by the interviewers at Columbia University. Once the transcripts are cleaned and final, both the transcripts and the interview summary sheets will be electronically transferred to the central study team at the University of Pennsylvania using a secure File Transfer Protocol site, where they will be uploaded and managed using a qualitative software package. The qualitative data from MTN-035 will include the IDI transcripts and the summary sheets detailing major points of interest regarding acceptability and adherence from each interview. The research team at the University of Pennsylvania will manage all qualitative data for the study. A convention for file naming will be developed, and all data will be labeled according to this process. The research team will save all versions of the files on a secure, password-protected server.

